## Methods.

### Design:

This is a proof-of-concept, prospective, randomized clinical trial for safety of TheraGauze-tobramycin in adult subjects who present to Emergency Department settings for care of skin abscess requiring incision and drainage. A control, standard of care, arm is included to provide some data with respect to the side effect profile of current furunculosis management for comparison.

Two arms are proposed for this study:

1. Incision + TheraGauze+tobramycin packing (no systemic antibiotics)
2. Incision + standard iodoform wick or plain cotton wick packing ( $\pm$  p.o. antibiotics)

Anti-microbial TheraGauze (saturated with tobramycin ophthalmic solution at 3 mg/ml) will be packed into the drained wounds of the subjects in the study arm. The control arm will receive current standard of care wound packing with a choice of iodoform wick or plain cotton wick, based on the preference of the ED physician. After packing, the wound excess TheraGauze or wick will be cut away. The ED physicians have the option to prescribe an oral antibiotic or not,

according to their preference. The following oral antibiotic choices are available for subjects in the control arm only:

- Bactrim (TMP/SMX)
- Vibramycin (doxycycline)
- Cleocin (clindamycin)

Antibiotics will be purchased by subjects from their local pharmacy.

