Protocol Title: Safety and Tolerability Study of Antimicrobial TheraGauze for Skin Abscess - Pilot Study

Phase of Study: I

Version date: 30March2017

Funding for this project is from the Department of Defense, through Soluble Systems, LLC

Principle Investigator: [name]  
Eastern Virginia Medical School  
[name]  
[name]  
[contact]  
[contact]  
[contact]  
Email: [[contact]](mailto:[contact])

Institutional Review Board: Eastern Virginia Medical School IRB (FWA00003956)

**Background.** Skin infections resulting in abscess, furunculosis, have become increasingly common in the past decade with the rapid emergence of community-associated methicillin-resistant *Staphylococcus aureus* (MRSA). The increasing incidence of these skin infections has stressed the medical system at the primary care, urgent and emergent care levels at significant cost. Methicillin-resistant *S. aureus* (MRSA) killed 18,650 Americans in 2005, exceeding the number of deaths attributable to HIV/AIDS (Klevens, Morrison et al. 2007). MRSA infections were identified for 368,600 hospital stays in the U.S. in 2005 for an estimated \$5 billion in hospitalization costs (Healthcare Cost and Utilization Project, DHHS).

The primary endpoint of the study is to evaluate the safety of and identify side effects of TheraGauze/tobramycin wound packing compared with standard of care management for cutaneous abscesses requiring incision and drainage. Current standard of care in most emergency and urgent care settings for community-acquired skin abscess is incision and drainage followed by packing with cotton wick ( $\pm$  iodoform) and anti-MRSA systemic antibiotics given orally for 5 – 7 days (Mistry, Weisz et al. , LoVecchio, Perera et al. 2009). Commonly prescribed oral antibiotic regimens include trimethoprim-sufamethoxazol, doxycycline, and clindamycin. Common side effects from these systemic antibiotics include diarrhea (~20%), nausea, and rash (Powell and Wenzel 2008). Uncommon but severe side effects include *C. difficile* colitis, Stevens-Johnson Syndrome, toxic epidermal necrolysis, hepatitis, and aplastic anemia (Bell, Foster et al. , Mistry, Schwab et al. 2009).

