The primary likely benefit of this novel therapeutic strategy is avoiding the side effects of systemic antibiotics that cause significant additional morbidity and medical expense. Other possible benefits of this novel strategy are improved wound healing time and less scar formation. This work will capitalize on the polymer structure of TheraGauze that provides a platform for fluid redistribution within the wound bed without causing skin maceration (Landsman 2008). We have developed an antimicrobial form of TheraGauze by loading TheraGauze with tobramycin (TheraGauze+tobramycin). Prior in vitro testing demonstrated potent and sustained antibacterial activity for TheraGauze+tobramycin against a wide range of bacterial pathogens, including all strains of community-associated MRSA tested (Echague, Hair et al. 2010). Lack of systemic absorption is a well-established property of tobramycin. Thus, high concentrations can be delivered locally in the wound greatly exceeding typical minimum inhibitory concentrations (MICs) without concern for systemic toxicity. Additionally, tobramycin is a highly bactericidal antimicrobial compound. Tobramycin is rarely used as a systemic antibiotic now having been largely replaced by fluoroquinolones. Therefore, selective pressure that could promote development of antibiotic resistance and compromise systemic antibiotic therapy is not a concern.

Tobramycin has been used for many years both as topical therapy applied to the eyes as well as in surgical wounds as tobramycin-containing polymethacrylate beads. Topical application of tobramycin to cutaneous wounds has also been reported without evidence of local or systemic toxicity. Andrew et al reported application of 3% (w/v) tobramycin with dexamethasone (i.e., Tobradex) ointment applied to post dermatological procedure surgical wounds twice-a-day for 2 weeks. Eighteen human subjects were enrolled and no local or systemic side effects were noted (Andrew, Luecke et al. 2012)

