In 2003 Simplex P with tobramycin was the first FDA approved antibiotic impregnated bone cement ([www.stryker.com](http://www.stryker.com)). Preparations of tobramycin-impregnated bone cement appear to generally range from 1g to 1.2g in 20 ml (50 – 60 mg/ml) (Sterling, Crawford et al. 2003, McLaren, McLaren et al. 2008). Tobramycin is reported to be the antibiotic of choice for bone cement for more than 75% of orthopedic surgeons (Fish, Hoffman et al. 1992) with excellent local tobramycin levels and minimal systemic tobramycin levels (Soto-Hall, Saenz et al. 1983, Eckman, Henry et al. 1988, Davies and Harris 1991, Pritchett and Bortel 1992, Brien, Salvati et al. 1993, Sterling, Crawford et al. 2003, McKee, Li-Bland et al. 2010). Despite the extensive literature on tobramycin bone cement there are no mentions of local toxicity. It is notable that so little toxicity has been reported given the significantly varying amounts of tobramycin cement are used for different types of orthopedic procedures and depending on the amount of bone being replaced. The wounds the tobramycin cement are in deep tissue spaces that are highly vascular. In contrast, TheraGauze/tobramycin will be placed into small (2 - 10ml) cutaneous abscesses where the bacterial infection has been walled off to protect the body from spread.

Tobramycin has also been used as a topical ophthalmic preparation for many years both as an ointment and drops (3 mg/ml) (e.g., Tobrex). Despite the very sensitive nature of topical application to the eye the package insert for Tobrex notes <1% hypersensitivity and eye or eyelid irritation is 3%, which is a typical rate for antibiotic eye drops. Additionally, Tobramycin eye drops (3 mg/ml) have been shown to have no adverse effects on reepithelialization and be well tolerated after penetrating keratoplasty (Blavin, Sauer et al. 2012)

Thus, there are several decades of human data demonstrating the safety of tobramycin when used topically for cutaneous and ocular wounds and in surgical wounds. The data suggests that local or systemic toxicity is extremely rare when tobramycin is used in these ways.

**Primary Endpoint.** The primary endpoint of the study is to evaluate the safety of and identify side effects of TheraGauze/tobramycin wound packing compared with standard of care management for cutaneous abscesses requiring incision and drainage.

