**Study Treatments**

Visit 1 - Day 1:

- Informed consent will be obtained from subject.
- Review of Eligibility Criteria (Inclusion/Exclusion)
- Randomization to Treatment Arm
- Contact Information to include phone number(s), address, and primary care provider information will be collected.
- Treatment and discharge with instructions to return to the ED for reevaluation per routine care. The typical schedule is for the patients to return to the ED 2 days after initial wound care (Study Day 3 -1/+2).

The following information will be collected and recorded on a hard copy Case Report Form at this visit.

- Subject ID number
- Demographics

- Date of visit
    - Age in years and months at time of enrollment
    - Race (white, non-white)
    - Ethnicity (Hispanic or non-Hispanic)
  - Medical history
    - Chronic medical conditions:
      - \_\_\_\_\_
      - \_\_\_\_\_
      - \_\_\_\_\_
      - \_\_\_\_\_
    - Concomitant Medications
      - \_\_\_\_\_
      - \_\_\_\_\_
      - \_\_\_\_\_
      - \_\_\_\_\_
    - Allergies to medications
      - \_\_\_\_\_
      - \_\_\_\_\_
      - \_\_\_\_\_
  - Characteristics of symptoms and history
    - Duration of symptoms (number of days)
    - Fever > 38.0°C duration? (y/n, record number of days febrile at home prior to ED visit)
    - Fever > 38.0°C in ED? (y/n, record temp)
    - Spontaneous drainage (y/n)
    - Prior skin abscess (y/n)
    - Immediate family history (parent, sibling, child) of skin abscess (y/n)
  - Abscess characteristics
    - Erythema at widest diameter (mm)
    - Abscess induration at widest diameter (mm)
    - Abscess location (e.g. trunk, extremity, buttocks, perineal, axilla, head/neck)
  - Procedure information
    - Diameter of wound after incision (mm)
    - Treatment Arm:
      1. Anti-microbial TheraGauze (TheraGauze/tobramycin)
      2. Iodoform wick/ plain cotton wick
    - Length of packing used (mm)
  - Laboratory Assessments – Per standard clinical care the abscess contents will be sent for routine Gram stain, bacterial culture and susceptibility testing as dictated by the patient's insurance and ED policy.
    - Obtain results when available
  - If patient is to receive iodoform wick/plain cotton wick then the care provider will have the option of prescribing a p.o. antibiotic, as is frequently done in these clinical settings. The following oral antibiotic choices are available for subjects in the control arm only:
    - Bactrim (TMP/SMX)
    - Vibramycin (doxycycline)

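### The whole-arm comparison tests the antibiotic-avoidance rationale only in diluted form, and because intended regimen is not recorded before allocation, no antibiotic-specific contrast is protected by randomisation

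*Combined protocol and SAP*

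**What the plan says.** The primary endpoint, given in the Background and again under Primary Endpoint, concerns safety and "side effects of TheraGauze/tobramycin wound packing compared with standard of care management". Under Design, the role of the comparator is modest: "A control, standard of care, arm is included to provide some data with respect to the side effect profile of current furunculosis management". Arm 2 is wick packing with or without oral antibiotics. "The ED physicians have the option to prescribe an oral antibiotic or not", and the three listed drugs are open to control subjects only.

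In Study Treatments, Visit 1 lists randomisation ahead of treatment. If the subject is to receive a wick, "then the care provider will have the option of prescribing a p.o. antibiotic". The choice therefore arises after the arm is known. Visits 2 and 3 ask, without restriction by arm, whether an oral antibiotic was prescribed, whether it was filled and how many doses were taken. No item asks, for every subject, what would have been prescribed under control.

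The Statistical Analysis Plan compares the two treatment groups. It has no stratum, subgroup or adjustment for antibiotic use.

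On rationale, the Background says: "The primary likely benefit of this novel therapeutic strategy is avoiding the side effects of systemic antibiotics". It describes standard of care as including "anti-MRSA systemic antibiotics given orally for 5 – 7 days", without the optional sign that Design attaches, and adds: "Common side effects from these systemic antibiotics include diarrhea (~20%), nausea, and rash".

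**The concern.** The argument for the product is that patients are spared antibiotic side effects. Only controls whose physician chooses to prescribe are exposed to those side effects, so the difference between arms shrinks with every control left untreated. A small observed difference could mean that few side effects were avoided, or only that few controls were prescribed antibiotics.

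The natural next step, setting antibiotic-treated controls against the TheraGauze arm, does not resolve this. Those controls were picked by physician preference after allocation. If the group is defined by intake, they are picked by patients too, since subjects buy the drug themselves. Their counterparts in the TheraGauze arm cannot be identified, because nobody recorded who would have been prescribed an antibiotic. That information cannot be recovered once the arm is known.

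**Working it through.** **Plan's own figures.** Study Size gives 100 randomised 2:1 and 50% retention. 100 × 0.5 = 50 completers, as stated. A 2:1 split gives about 67:33 randomised and 33:17 completing. No power, effect size or numerical equivalence margin is given, so there is nothing further to reproduce.

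**Inputs.** Diarrhea on antibiotics: 20% (Background). Diarrhea without antibiotics, *b*: not given; 2% assumed, with 0% and 5% as the range. Share of controls prescribed antibiotics, *q*: not given; 30% to 90% assumed.

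**Dilution.** The control rate is 0.20*q* + *b*(1 − *q*) and the TheraGauze rate is *b*, so the whole-arm excess is *q*(0.20 − *b*). In percentage points:

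| *q* | *b* = 0% | *b* = 2% | *b* = 5% |
|---|---|---|---|
| 30% | 6.0 | 5.4 | 4.5 |
| 50% | 10.0 | 9.0 | 7.5 |
| 70% | 14.0 | 12.6 | 10.5 |
| 90% | 18.0 | 16.2 | 13.5 |
| 100% | 20.0 | 18.0 | 15.0 |

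**Size of the intended-antibiotic stratum at *q* = 70%.** Randomised: 67 × 0.7 ≈ 47 versus 33 × 0.7 ≈ 23. Completers: 33 × 0.7 ≈ 23 versus 17 × 0.7 ≈ 12.

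**Precision among completers at *q* = 70%, *b* = 2%** (unpooled 90% CI):
- Stratum: expected difference 18 points; half-width 1.645 × √(0.20 × 0.80/11.9 + 0.02 × 0.98/23.1) = 1.645 × 0.1196 = 19.7 points.
- Whole arms: control rate 0.7 × 0.20 + 0.3 × 0.02 = 14.6%; expected difference 12.6 points; half-width 1.645 × √(0.146 × 0.854/17 + 0.02 × 0.98/33) = 1.645 × 0.0890 = 14.6 points.

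In both cases the half-width exceeds the expected difference.

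**Power** (two-sided 0.05, normal approximation; cells are small, so indicative only), *q* = 50%, *b* = 2%: whole arms 50% and stratum 58% if all 100 are observed; 32% and 37% among completers. Over the assumed ranges of *b* and *q*, the stratum never has less power than the whole-arm contrast.

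**Selection illustration** (all inputs assumed; outcome is treatment failure, no true treatment effect). Let 40% of abscesses be severe, with failure risk 30% if severe and 10% if mild. The spurious difference between antibiotic-treated controls and all TheraGauze subjects is (share severe among the treated − 0.40) × (0.30 − 0.10):
- Prescribing to 80% of severe and 60% of mild: 0.32/0.68 = 0.471, giving 1.4 points.
- 90% and 40%: 0.36/0.60 = 0.60, giving 4.0 points.
- 95% and 20%: 0.38/0.50 = 0.76, giving 7.2 points.

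**The case against.** The strongest reply is that the plan never promises a comparison with antibiotics. Its endpoint is against standard of care, the control arm is there to give some descriptive data, and the SAP contains no contrast with antibiotic-treated controls. For that question the prescribing mix belongs to the comparator. This stands. A reader might infer that the trial's main comparison is non-randomised, or that TheraGauze versus antibiotics is its stated target. The documents support neither reading: antibiotic avoidance is rationale, not endpoint.

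A reader might also infer that treated controls are sicker. The documents speak only of physician preference. Eligibility narrows the range of severity, and erythema, induration, fever and symptom duration are recorded at Visit 1 in both arms, so some adjustment is possible. Nor is it shown that abscess severity would drive diarrhea. This stands too: selection by preference is documented, while confounding by severity is an inference. Adjustment for recorded features still would not identify who would have been prescribed an antibiotic.

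A third reply is that the remedy fails as a randomised comparison if the next assignment can be foreseen. The Randomization section illustrates a repeating 1,1,2 sequence on a prepared list and mentions no concealment. This is correct and is a condition on the fix. It is also fair that intention is not exposure: unfilled prescriptions leave the stratum diluted.

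**Conclusion.** The point holds as an inexpensive improvement to a Phase I pilot, not as a fault in its stated comparison. The whole-arm contrast answers the question the protocol asks. The antibiotic-avoidance rationale is seen only in diluted form: about 5 to 16 points of excess diarrhea at prescribing shares of 30% to 90%, against 18 with all controls treated. This rests on the protocol's 20% and an assumed 2% background; the prescribing share is also assumed. Changing the background to 0% or 5% alters the sizes but not the pattern.

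Any contrast restricted to antibiotic-treated controls is physician-selected. The illustrative 1.4 to 7.2 points concern treatment failure under assumed inputs and do not estimate bias in side effects. It would also go too far to call the proposed stratum randomised without qualification, or to expect a powered test from it. The SAP uses data collected before withdrawal, so the usable numbers lie somewhere between the randomised and completer counts.

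**What to change.** 1. Add one line to the Visit 1 case report form, completed for every subject before allocation is opened: if assigned to control, oral antibiotic yes or no, and which wick type.
2. Keep the whole-arm comparison as the main one.
3. Add to the SAP one supporting, descriptive table of antibiotic-type side effects (diarrhea, nausea, rash) by arm within the intended-antibiotic stratum, with confidence intervals. Define the stratum by intended, not actual, prescription. Report filling and doses alongside it, and the intended prescribing share.
4. Use an unpredictable, concealed allocation list in place of the illustrated repeating sequence. Without this the recorded intention can be shaped by the foreseeable next arm, and the stratum loses its protection.

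The change alters no treatment and leaves the physician's choice as it is. The direct cost is one form line and one table; the concealed list is an added requirement. The downside is the imprecision shown above, plus residual dilution from unfilled prescriptions. A further gain is an estimate of the intended prescribing share, which a later trial would need for its sample size.

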#### TheraGauze/Tobramycin creation

1. TheraGauze commercial preparation will be dehydrated in the factory and spiral dye to yield a 17 cm strip of TheraGauze of uniform width. After cutting the dry TheraGauze will be packaged and sterilized by gamma radiation. This follows all of the current steps of manufacturing only adding dehydration and cutting steps.
2. Dried TG packages will be provided to the Sentara Norfolk General Hospital (SNGH) Emergency Department (ED).
3. Commercial 10 ml vials of tobramycin ophthalmic solution (3 mg/ml) for human use will be provided by the SNGH pharmacy and stored in the temperature monitored med room in the SNGH ED. Each vial will be opened only once and then discarded.
4. After randomization has been determined, a new 10 ml vial of tobramycin ophthalmic solution will be opened and added to newly opened TG in a sterile dish by the study coordinator and allowed to rehydrate to saturation (5 minutes). Maximal saturation of the 17 cm TheraGauze strip is achieved with only 7 ml of solution.
5. The wound will be packed with the TheraGauze/tobramycin strip and any excess length will be cut off, measured and discarded.

#### Methods:

*Study Population:*

Subjects from the Hampton Roads region of southeastern Virginia will be recruited from the hospital emergency department site staffed by EVMS physicians at Sentara Norfolk General Hospital.

*Study Size:*

We anticipate screening 200 patients in order to enroll and randomize 100 subjects. Subjects will be randomized 2:1 to the TheraGauze+tobramycin or iodoform wick/ plain cotton wick, respectively. We anticipate 50 participants completing the study. The 50% retention rate is typical for emergency department populations.

*Subject Eligibility:*

Inclusion criteria:

- Ages  $\geq 18$  to  $\leq 65$  years at time of enrollment
- Subject has skin abscess (furuncle) requiring incision and drainage
- Erythema surrounding abscess
- Induration of  $\geq 2$ cm in maximal diameter
- Fluctuance or purulent head evident
- Tenderness at abscess
- No or mild fever  $\leq 38.5^{\circ}\text{C}$
- Male or female
- Ability to read and understand the English language at a level sufficient to provide informed consent and comply with study requirements
- Subject is willing and able to comply with all study requirements

Exclusion criteria:

- Systemic illness or deep-seated infection requiring inpatient admission (i.e. hypotension, tachycardia, or tachypnea)
- Deep seated infection requiring referral to surgery
- Subject requires intravenous antibiotics for suspicion of systemic spread of infection (i.e. suspicion of bacteremia)
- Extensive cellulitis extending  $> 6$ cm beyond the area of induration
- Fever  $> 38.5^{\circ}\text{C}$
- Allergy to any aminoglycoside antibiotic, sulfamethoxazole-trimethoprim, doxycycline, clindamycin.
- An underlying medical condition that impairs normal immune function (e.g. AIDS, cancer, diabetes, lupus, rheumatoid arthritis, organ or marrow transplantation, ulcerative colitis, Crohn's disease)
- Subject is pregnant or breastfeeding and/or a woman of childbearing potential who is not surgically sterile, not at least 2 years postmenopausal, or does not practice contraception methods, unless sexually abstinent for the duration of the study.
- Subject has any medical or psychiatric condition, in the opinion of the investigator, could jeopardize the subject's health or compromise the subject's ability to participate in the study.
- Subject has prior treatment with antibiotics in the preceding 7 (seven) days.
- Currently taking or has taken oral or injection steroid medication (e.g. prednisone or Medrol Dosepak) in the past 30 (thirty) days

- Injection medications (Remicade, Humira, Cimzia, Simponi) other than vitamin (B6)
- Currently taking or has taken immune suppressing medications (e.g. methotrexate, Prograf, CellCept, Rapamune) in the past 30 (thirty) days
- Currently taking or has taken medications to treat cancer in the past 30 (thirty) days
- Subject is currently participating or has participated within the last two months in any study of an investigational drug or device.

*Recruitment and Retention:*

Subjects who present to Emergency Department setting for care of skin abscess requiring incision and drainage will be approached by on-site Study Coordinators for enrollment. The study coordinators and physician investigators are trained in obtaining informed consent. The potential subjects will be able to discuss participation with any family-member present, but due to the need for prompt treatment, the subject will need to make a decision regarding participate at the time of the Emergency Room visit. Upon meeting eligibility criteria and willingness to participate, subjects/LARs will provide informed consent. Complete demographic information to include residential and telephone contact information will be obtained. Prior relevant medical history and usual primary care contact information will also be collected. A medical information release will be obtained from the subject so that outcomes data can be collected related to additional unscheduled visits or adverse events cared for outside the emergency department setting.

*Women and minority participation:*

Adults up to 65 years of age will be enrolled regardless of gender and minority status as long as they are fluent in English.

*Randomization:*

A study subject identification number will be assigned. Subjects will then be sequentially randomized to one of two treatment arms upon enrollment in a 2:1 ratio, using a prepared list. Each subject's name will be recorded on the list next to his/her assigned subject number and randomization. For example, the first subject enrolled will be randomized to Treatment 1; the next enrolled subjects will be enrolled to Treatment 1; the third subject to Treatment 2. The fourth subject will be randomized to Treatment 1 and so on.

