#### **ROLES OF RESEARCH TEAM MEMBERS**

Physician investigators and Emergency Room staff will identify potential subjects and will notify the coordinator. The coordinator will explain the study and she or the physician will obtain informed consent. The physician will collect medical history culture the wound, and care for the wound per standard of care, using TheraGauze with tobramycin or standard gauze per randomization. The coordinators will ensure that all data are collected and recorded in the study chart, collect lab results, schedule follow-up appointments and make telephone contacts. Routine cultures and sensitivities will be performed in the hospital laboratories. The research lab staff will perform quantitative analysis. Coordinators and lab staff will enter data into the database. The statistician, with the PI, will analyze the results. The PI will oversee all of the above activities as well as performing most of the Visit 3 clinical assessments. and report findings to the sponsor.

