#### **RESEARCH MONITOR.**

All Serious Adverse Event (SAE) reports will be sent to the Research Monitor, [name], within 24 hours. The Research Monitor will also review subject charts for safety on a 3 to 6 month basis, assessing for evidence of tolerability or superiority/inferiority between the arms, and will discuss her findings with the PI. The Research Monitor may discuss the protocol with the investigators, interview subjects, and consult with others outside the study about the research. She shall have the authority to stop the protocol, remove subjects from the protocol, and take any necessary steps to protect the safety and well-being of subjects until the IRB can assess the Monitor's report. The Research Monitor shall have the responsibility to promptly report her observations and findings to the IRB or other designated official. The Research Monitor is required to review all unanticipated problems involving risks to subjects or others, serious adverse events and all subject deaths associated with the protocol and provide an unbiased written report of the event. At a minimum, the research monitor must comment on the outcomes of the event or problem and in the case of a serious adverse event or death, comment on the relationship to participation in the study. The research monitor must also indicate whether he/she concurs with the details of the report provided by the principal

investigator. Reports for events determined by either the investigator or research monitor to be possibly or definitely related to participation and report of events resulting in death must be promptly forwarded to the USAMRMC ORP HRPO.

Study Visit Schedule:

PROCEDURE	VISIT 1	VISIT 2	VISIT 3
	Screening/Day 1	Day 3-1/+2 days	Day 7±2 days
Consent	X		
Inclusion/exclusion	X		
Demographics	X		
Medical history	X		
History and current symptoms	X	X	X
Temperature, wound assessment	X	X	X
Culture abscess	X	X	
Randomization	X		
Apply wick	X		
Provide prescription if applicable	X		
Remove packing (if applicable)			
Follow-up phone call Day 2 (+2)	X		
Follow-up phone call day prior to Day 7 visit		X	

REFERENCES

Andrew, R., G. Luecke, S. Dozier and D. G. Diven (2012). "A pilot study to investigate the efficacy of tobramycin-dexamethasone ointment in promoting wound healing." *Dermatol Ther (Heidelb)* **2**(1): 12.

Bell, T. L., J. N. Foster and M. L. Townsend "Trimethoprim-sulfamethoxazole-induced hepatotoxicity in a pediatric patient." *Pharmacotherapy* **30**(5): 539.

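### The arm is assigned before incision and drainage with nothing to keep it from the operator, and the baseline millimetre measurements are not required to come first

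*Combined protocol and SAP*

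**What the plan says.** On timing, the Randomization paragraph states: "Subjects will then be sequentially randomized to one of two treatment arms upon enrollment in a 2:1 ratio, using a prepared list". Under Study Treatments, the Visit 1 list gives consent, then "Review of Eligibility Criteria (Inclusion/Exclusion)", then "Randomization to Treatment Arm", then contact details, then "Treatment and discharge with instructions to return to the ED for reevaluation per routine care". The Design section defines both arms as incision plus a packing. The inclusion criteria require an abscess that still needs to be opened.

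On preparation and treatment, the section on creating the TheraGauze/tobramycin strip says: "After randomization has been determined, a new 10 ml vial of tobramycin ophthalmic solution will be opened". The coordinator does this and lets the strip soak for 5 minutes. The Roles section has the physician "care for the wound per standard of care, using TheraGauze with tobramycin or standard gauze per randomization".

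On measurement, the Visit 1 case report form items include erythema and induration in millimetres, "Diameter of wound after incision (mm)" and the length of packing used. The Study Visit Schedule table prints the row "Temperature, wound assessment" and the abscess culture row above the randomization row.

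The documents describe no blinding and no withholding of the arm until the wound has been drained.

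**The concern.** Incision and drainage is background treatment common to both arms. It should be the same in both, so that differences afterwards can be put down to the packing and the antibiotic policy. An operator who knows that a TheraGauze subject will receive no systemic antibiotic has a plausible reason to open the abscess wider or drain it more fully. That influence arises after assignment, so a properly random and concealed list would not remove it.

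The primary endpoint is a safety comparison with standard care. The Adverse Reaction paragraph looks for local toxicity through increasing redness, increasing pain or a new rash at the wound, and counts a need for further drainage as progression of infection. The SAP also summarizes persistence or worsening of infection and the rate of healing, and plans equivalence tests between the arms. Surgical technique can plausibly act on local pain, redness, re-accumulation and healing. If technique follows the arm, the comparison mixes the packing with the technique.

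**Working it through.** The check is on the order of events. The plan states no figure for this point, so there is none to reproduce.

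1. **Is the arm assigned before incision?** Yes. Randomization happens on enrollment and is listed before treatment at Visit 1. Incision is a component of each arm in the Design section. Entry requires an abscess that has not yet been drained. These three statements together fix the order.

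2. **Is the abscess sized before assignment?** Against thresholds, yes. The eligibility review precedes randomization. It requires induration of at least 2 cm and surrounding erythema, and it excludes cellulitis reaching more than 6 cm past the induration. What stays open is when the millimetre values on the form are taken, and by whom. The form list does not settle this, because it is a list of items and not a sequence. It also contains chronic conditions, concomitant medication and drug allergies, several of which decide eligibility and must be known earlier. The row order of the schedule table is equally weak evidence.

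3. **Does anything before packing need the allocation?** No. By the Design section the arms differ only in the packing and in the option of an oral antibiotic. Both follow drainage.

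4. **Which recorded values fall after assignment?** The post-incision wound diameter and the packing length, necessarily. Visit 3 records wound diameter. Visit 2 records erythema and induration but no wound diameter. The post-incision value is therefore the only earlier counterpart to the Visit 3 diameter. It is not a pre-randomization covariate, so adjusting for it would not cleanly remove a difference caused by knowledge of the arm.

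5. **Can eligibility change after assignment?** Yes. Deep-seated infection needing surgical referral is an exclusion, and it may become apparent only when the abscess is opened. The SAP says how to handle withdrawal during treatment. It has no rule for a subject found ineligible between assignment and packing.

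6. **Would a later reveal work with the list as illustrated?** Not by itself. The Randomization paragraph gives the order 1, 1, 2, 1 and indicates that it continues. Repeating 1, 1, 2 over 100 subjects gives 33 full sets (33 × 3 = 99 subjects, 66 to TheraGauze and 33 to control) plus one further TheraGauze subject, so 67:33. That meets the 2:1 ratio, but anyone who knows the pattern and the count can foresee the next arm.

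**The case against.** A reader might infer that the arm is assigned before the abscess is measured at all, and that a physician who knows the arm makes every Visit 1 measurement. The documents do not support this. Sizing against the entry thresholds comes before assignment, the assessor of the millimetre values is not named, and the schedule table even prints wound assessment above randomization. The strip-preparation and Roles sections say that packing follows the allocation. Neither says that the operator already knows the arm when making the incision. Operator knowledge is an inference from the listed order and the absence of any safeguard.

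It is also fair to say that this is a Phase I pilot whose control arm is meant to supply some comparative side-effect data. Healing is not the primary endpoint, and the SAP lists it among the measures to be summarized descriptively. Several solicited events, such as diarrhea and nausea, do not plausibly depend on how an abscess is opened.

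These points limit the reach and certainty of the concern. They do not answer its core: assignment precedes drainage, nothing withholds the arm, and the local safety signals are among those that technique could affect.

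**Conclusion.** The concern holds in limited form, with medium confidence. The arm is assigned at enrollment, before incision and drainage, and the protocol neither keeps it from the operator nor requires the recorded erythema and induration values to come first. The extent of drainage and the post-incision diameter are therefore open to influence by knowledge of the arm. The outcomes at risk are local pain, redness, repeat drainage and healing.

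All 100 planned randomized subjects are exposed to this route. That describes exposure, not effect. The documents contain no figure from which to derive a difference in incision size between arms, or a number of subjects found ineligible at incision, so none is given here.

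The conclusion rests on two assumptions: that the Visit 1 steps from consent to treatment are carried out in the listed order, and that the operator can learn the arm once it is assigned.

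**What to change.** In the Randomization paragraph and the Visit 1 list, state this order:

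- erythema and induration are recorded in millimetres;
- incision and drainage is completed;
- the post-incision diameter is recorded;
- the existing eligibility criteria are reconfirmed;
- only then is the allocation revealed to the operator, and the time of reveal is recorded.

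Strip preparation and any prescription follow the reveal. Bring the Study Visit Schedule table into line.

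Replace the repeating 1, 1, 2 illustration with a concealed, unpredictable 2:1 list. Without that, a late reveal achieves little, because the operator could foresee the arm.

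The cost is protocol wording, one extra time field on the case report form, and a list prepared and held so that the next assignment cannot be seen. The practical downside is a wait of about 5 minutes after drainage, in TheraGauze subjects, while the strip rehydrates. If the sponsor prefers the present order, the protocol should justify it and acknowledge that the post-incision diameter is not a pre-randomization baseline.
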